Health sector cost will be primarily attributed to the cost of treatment delivered by the institution, NUH CDU. The gross charges for paediatrician review, IIP review and administering surveys and assessments for the children are consistent in both study arms. Only variable cost between both study arms will be included. The variable cost includes the clinic-based intervention charges and video-conferencing-based intervention charges across both arms. The assumption for health sector cost will be that participants from both arms attend all the review and assessment sessions as they are essential to the intervention plan. The only variability would be attributed to defaulted therapy sessions.

Direct Non-Healthcare Costs

Transportation Costs

Transportation cost will be estimated using the responses from the baseline cost survey administered to caregivers. The total transport cost per study arm (standard vs telerehab) will be calculated by multiplying the *observed number of clinic-based visits* (accounting for missed appointments/therapy sessions) with the average cost of transportation indicated by the caregiver multiplied by two to account for round-trip travelling.

Caregiver and other care costs

Costs from other sectors include care cost from attending courses, hiring domestic helpers and/or other forms of care support for the child. This information is obtained from the cost survey administered to the parents.

Indirect Costs

Productivity Loss

Productivity loss will be calculated using the human capital approach. The human-capital method takes the patient's perspective (in this case the parent's time) and counts any hour not worked as an hour lost.

² <https://yhec.co.uk/glossary/probabilistic-stochastic-sensitivity-analysis/>
TRAutism HSDP Protocol_Version 8_19/08/2022

Productivity loss in this study will be primarily attributed to the caregiver taking time off from work to attend treatment with the patient (their child) and applying intervention strategies with the child. The time spent by caregivers includes the following:

- i. time spent on travelling CDU for treatment (two-way trip);
- ii. time spent on therapy sessions (30mins for video-conference, 45mins for clinic-based);
- iii. employment charges

Outcomes

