We will examine the primary outcome, Mullen's Scale of Early Learning (MSEL) Early Learning Composite Score (ELC) as the key outcome of interest (i.e. the denominator for ICER). We will also examine the outcomes in VABS and JERI as outcomes of interest. Parameters for modelling for outcomes will be obtained from analyses specified in the previous section.

Input Data for Outcomes and Cost Data for the Model

The input data for the model from the survey administered is listed below in Table 2.

Table 2: Data Source and Parameters Estimates and Distribution for Cost-effectiveness Analysis

	Standard	Telerehab	Parameters Estimated	Distribution
Outcomes	Estimates from analysis from t-test/regression for: MSEL-ELC, VABS composite score and/or JERI	Estimates from analysis from t-test/regression for: MSEL-ELC, VABS composite score and/or JERI	Mean (SD) improvement in outcomes examined	Normal
Direct Healthcare Cost				
Attendance for therapy sessions	Number of clinic-based therapy sessions attended	Number of clinic-based and telerehab therapy sessions attended Telerehab consists of clinic-based sessions at the start of the program + telerehab sessions	Mean (SD) of therapy session attended across each study arm	Normal or gamma
Healthcare cost	Total cost of clinic-based therapy sessions	Total cost of clinic-based + telerehab therapy sessions	Number of visits * fixed cost per visit (standardized for FY2021/22)	Fixed
Direct Non-healthcare Cost				
Transport costs	Survey questions 
 • What mode of transport did you use to get here today? • How much did it cost? • Do you usually use this mode of transport to get to the clinic/CDU? • If no, what is your usual mode of transport? • How much did it cost? 	Survey question 
 • What mode of transport did you use to get here today? • How much did it cost? • Do you usually use this mode of transport to get to the clinic/CDU? • If no, what is your usual mode of transport? • How much did it cost? 	The total transportation cost incurred by participants will differ between study arms by nature of the mode of delivery. The actual transportation cost will account for two-way (round trip) and the observed visits (accounting for missed appointments for example)	Normal

			Transport Cost = Total no. of trips * Mean transport cost * 2	

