Caregiver and other care cost	
 [At review] Did you pay for help (courses, caregivers, domestic helpers) after learning about your child's diagnosis? How much did you pay? 	
 [At review] Did you pay for help (courses, caregivers, domestic helpers) after learning about your child's diagnosis? How much did you pay? 	
Assuming that the rate of care engagement is different in both study arms, the cost of engaging additional care.
 
Care cost = Probability of engaging additional care by group * mean cost care by groups
	
Probability of requiring additional care = Beta
 
Cost of added care = Gamma

Indirect Cost from Productivity Loss				
Baseline change in employment	
 Have you or other family members changed work hours because of your child's medical or developmental condition? 	
 Have you or other family members changed work hours because of your child's medical or developmental condition? 	
1 Yes, someone in the family stopped working 2 Yes, someone decreased his/her work hours 3 Yes, someone increased his/her work hours 4 No
 
We can base it off some assumption Assumption: 1 = 1.0 FTE Reduction 2 = 0.5 FTE Reduction 3 = 0.5 FRE Increase
	
Baseline anticipated change in employment	
 [at baseline] Do you foresee the need to adjust your employment situation in light of this intervention? 	
 [at baseline] Do you foresee the need to adjust your employment situation in light of this intervention? 	
1 Yes, reduce number of hours at work 2 Yes, make arrangements to work remotely
	

			
3 Yes, find a different job which allows me to spend more time with my child
 
4 Yes, taking unpaid leave
 
5 Yes, take time off
 
6 Yes, Others
 
7 No
	
Follow-up change in employment	
 • [at review] Have there been any changes to the employment arrangement at home due to the beginning of the intervention? • What is your monthly income now? 	
 • [at review] Have there been any changes to the employment arrangement at home due to the beginning of the intervention? • What is your monthly income now? 	Same as above	

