Follow-up time spent on intervention for caregivers	
 • In the past month, on average how much time (in hours) do you spend engaging (Speaking to, playing with, communicating with, doing activities) with your child per day? • In the past month, on average how much time (in hours) do you spend applying strategies learnt through the intervention with your child per day? 	
 • In the past month, on average how much time (in hours) do you spend engaging (Speaking to, playing with, communicating with, doing activities) with your child per day? • In the past month, on average how much time (in hours) do you spend applying strategies learnt through the intervention with your child per day? 	
Productivity loss in the time spend on delivering intervention to child
 
Time (in hour) spent on engagement with child + apply strategies learnt with child * hourly income of parent surveyed
	

Transport	
 • [baseline] How long did it take you to get to the clinic/CDU today? • Does it normally take you this long? • If no, how long do you usually take? 	
 • [baseline] How long did it take you to get to the clinic/CDU today? • Does it normally take you this long? • If no, how long do you usually take? • [At review] How long does it take for you to set up the computer before each telerehab session? 	Productivity loss in travelling time Time (in hour) required to travel to CDU today * 2 (two-way trip) * hourly income of parent surveyed	
------------------	-------------------------------------------------------------------------------------------------------------------------------------------------------------------------------------------------------------------------	------------------------------------------------------------------------------------------------------------------------------------------------------------------------------------------------------------------------------------------------------------------------------------------------------------------------------------	--------------------------------------------------------------------------------------------------------------------------------------------------	--

Data Cleaning Methodology and Approach

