The surveys administered were open ended and the quality of the data obtained is variable. The approaches and steps to standardise the cleaning of data for analysis are listed in the table below.

Data entry type	Approach	Example
Range of data indicated "3000-5000"	The average value between the maximum and the minimum data will be calculated	"3000-5000" $\rightarrow (3000+5000/2) \rightarrow 4000$ "4k to 6k" $\rightarrow (4000+6000/ 2) \rightarrow 5000$
Undefined boundaries "2000+"	The operators (~, +, ++, "plus) will be removed and the numeric value will be referenced instead	"2k+ to 3k+" $\rightarrow (2000+3000/2) \rightarrow 2500$ "7+" $\rightarrow 7$ "3k~ " $\rightarrow 3000$
Variable string responses "1hr on weekday, 5hr on weekends"	Value will be taken in reference to the question	Total time spent with child per week: "1hr on weekday, 5hr on weekends" $\rightarrow (1*5) + (5*2) = 15$ Average time spent with child each day: "1hr on weekday, 5hr on weekends" $\rightarrow [(1*5) + (5*2)]/7 = 2.14$
Missing / Not Applicable "-", "N/A", "0", "Not Applicable", "NA", "None", "Null", or "INF",	Converted to missing/empty responses	"-", "N/A", "0", "Not Applicable", "NA", "None", "Null", or "INF" \rightarrow NA
Out of range values	Values that are out of range e.g. 20-30 hours for time spent with the child daily	Replace with NA, treat as missing variable

Evaluation Management

This evaluation will be conducted by the NUS Centre for Health Services and Policy Research (CHSPR) and the research team at CDU.

Evaluation Time Frame

Table 3: Evaluation Time Frame from Protocol Version 6.0 dated December 2019

Time from project start date	Phase	Activity	Milestone
Year 1 Q1	Program preparatory phase	Manpower recruitment Clinical training in FSC	
Year 1 Q2	Program development & stabilization phase	Adapt and finalize Telerehab service model for Singapore context. Conduct feasibility study with 6 children and families	Feasibility study report and review
Year 1 Q3-Q4	Implementation	Enrolment and data collection for Year 1	
Year 2 Q3-Q4	Preliminary analysis of Year 1 data	Analysis of Year 1 data including Year 1 follow-up	Interim Report
Year 2 Q1-Q4	Implementation	Enrolment and data collection for Year 2	
Year 3 Q1-Q4	Implementation	Enrolment and data collection for Year 3	
Year 4 Q2-Q3	Final Analysis	Consolidation and analysis of final data including all follow-up data	Final Report

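### The survey cleaning rule turns genuine zero answers into missing values, which inflates mean fares, hours and income in the cost analysis

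*Combined protocol and SAP*

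**What the plan says.** The section Data Cleaning Methodology and Approach says the survey answers were open-ended and of variable quality, and gives a table of recoding rules. The row for missing or not-applicable entries covers a dash and "N/A', '0', 'Not Applicable', 'NA', 'None', 'Null', or 'INF". The action is "Converted to missing/empty responses". The row makes no distinction between questions. Only the row on variable text answers refers back to the question asked. How the resulting missing values are to be handled is not described.

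The rule feeds Table 2 of the cost-effectiveness section:

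- **Fare.** Parents are asked "How much did it cost", and the formula is "Transport Cost = Total no. of trips * Mean transport cost * 2". The Transportation Costs section says the trips are the "observed number of clinic-based visits".
- **Strategy time.** At review, parents report how many hours they "do you spend applying strategies learnt through the intervention with your child per day".
- **Income.** At review they are asked "What is your monthly income now". Hourly income then values the time in both productivity formulas.
- **Paid care.** "Care cost = Probability of engaging additional care by group * mean cost care by groups", with a Beta distribution for the probability and a Gamma distribution for the cost.
- **Travel time.** The productivity loss is one-way time, doubled, times hourly income. No number of visits appears. Telerehab parents are also asked how long set-up takes before a video session, but no formula uses the answer.

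**The concern.** A parent who walks to the clinic, a parent who applied no strategies in the past month and a parent without earnings can each truthfully answer 0 or None. The rule removes these answers, and the mean of what is left is too high. For fares this matters to the comparison, because the mean is multiplied by a trip count that differs widely between arms.

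The Cost-Effectiveness Analysis section rests its conclusion on whether telerehab saves costs, and its societal view includes travel and parental time. These are the inputs that the rule distorts. The probabilistic sensitivity analysis would not expose the problem, since it draws values around the means already estimated.

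The travel-time formula raises a second, smaller question. If it lacks the visit count that the fare formula has, it may leave out the saving that telerehab is designed to produce.

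**Working it through.** **Plan's own figures.** The worked examples in the cleaning table reproduce: (3000 + 5000)/2 = 4000, (4000 + 6000)/2 = 5000, (2000 + 3000)/2 = 2500, 1×5 + 5×2 = 15 hours a week, and 15/7 = 2.14 a day. The three range examples need the sum bracketed before dividing, which the table does not print. Table 1 also reproduces: 16×45 = 720 min of therapy in the standard arm, and 2×45 + 16×30 = 570 min in the telerehab arm.

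**Effect of deleting zeros.** Let f be the share of true zeros and m the mean of the positive answers. The true mean is (1 − f)m, and the rule reports m. The ratio is 1/(1 − f). The documents give no value of f, so 10% to 30% is an assumption.

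**Fares.** Inputs: 16 and 2 clinic therapy sessions (Table 1), two one-way fares per visit (Table 2). The difference is 2 × (16 − 2) = 28 one-way fares per family. Reviews and assessments attended equally in both arms cancel when f is the same.

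| Assumed f, both arms | 1/(1 − f) | Difference under the rule, in true mean fares |
|---|---|---|
| 10% | 1.11 | 28/0.9 = 31.1 |
| 20% | 1.25 | 28/0.8 = 35.0 |
| 30% | 1.43 | 28/0.7 = 40.0 |

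Similar shares are a reasonable expectation, because the fare comes from the baseline survey in randomised arms. If the shares differ, growth is not guaranteed. With equal true mean fares, 10% zeros in the control arm and 30% in the telerehab arm, the difference is 32/0.9 − 4/0.7 = 29.8. With 5% and 30% it is 32/0.95 − 4/0.7 = 28.0, so there is no inflation.

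**Strategy hours.** Suppose 10% of one arm and 30% of the other report zero, and everyone else reports 1 hour. The true means are 0.9 and 0.7 h a day, a difference of 0.2 h. Under the rule both means are 1 h and the difference is 0. Reversing the shares reverses which arm is favoured, so the direction cannot be stated in advance. The same holds for income.

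**Travel time.** Read literally, the formula gives 2 × (one-way time) × (hourly income), whether a family makes 16 clinic visits or 2. With a visit count, the therapy-visit difference is 14 round trips. At an assumed 0.5 to 1 h one way, that is 14×2×0.5 = 14 h to 14×2×1 = 28 h per family.

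**Set-up time.** At an assumed 5 to 15 min for each of 16 video sessions, the unused cost in the telerehab arm is 16×5/60 = 1.3 h to 16×15/60 = 4.0 h.

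**The case against.** *Some zeros are not real zeros.* Table 2 has follow-up items that apply only if the preceding answer is no (usual mode of transport and its fare, usual travel time). A 0 in a skipped item probably means not applicable, and a zero travel time to the clinic is implausible. Keeping every 0 as a number would replace one error with another. This stands, and it shapes the fix.

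*The care-cost row is already sound.* It is a two-part model with a positive cost distribution. Dropping zero amounts is right there, provided the probability comes from the yes/no item. This also stands.

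*The travel-time formula may be a unit cost.* The section on probabilistic sensitivity analysis lists number of visits among the parameters, so multiplication may be intended. That is possible, but Table 2 does not state it, although the fare row does.

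*The sizes are assumed.* True. The factor 1/(1 − f) is exact, but f is unknown.

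Two stronger readings are not supported:

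- A reader might carry the 10 control sessions from Protocol Deviation and Per-protocol Analysis into the cost model and infer that the parental-time difference changes sign. The cost model uses 16 sessions and 720 against 570 min (Table 1), so session time alone favours telerehab by 150 min, and fares use observed attendance. Travel, session and set-up time are in any case a subtotal. Home practice at the encouraged 2 h a week over 40 to 60 weeks is 80 to 120 h per arm, and a 5% arm difference in it would be 4 to 6 h.
- A reader might infer that adding engagement hours to strategy hours is an error. The Productivity Loss section describes its scope as primary and inclusive rather than exhaustive, and the missing brackets match the loose notation of the cleaning table.

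**Conclusion.** The cleaning rule is wrong as written for the fare, strategy-hours and income questions. It inflates each mean by 1/(1 − f), or 11% to 43% if 10% to 30% of answers are true zeros. For fares, with similar shares in both arms, the apparent telerehab saving grows by the same factor, from 28 one-way fares per family to between 31 and 40. For strategy hours and income, the direction of the effect on the arm difference is unknown.

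The travel-time formula is incomplete rather than shown to be wrong. Taken literally, it removes the travel-time saving, while leaving out set-up time favours telerehab. These gaps and the fare inflation do not all push the same way, so no net direction is claimed.

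The point should be settled before the final analysis. It reaches only societal-perspective inputs. The direct medical cost comparison (visits times a fixed charge) and the MSEL non-inferiority test are unaffected. The conflict between 16 and 10 control sessions is a separate per-protocol matter, and those passages must be reconciled in their own right.

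**What to change.** 1. Apply the missing-value rule by question. Keep 0, and None where it naturally means zero, as numeric zero for the fare actually paid, for strategy and engagement hours, and for income.
2. Treat 0 as missing or not applicable in conditional follow-up items that the preceding answer shows were skipped, and for travel time to the clinic. Convert only true non-response codes to missing, and state how missing values are then handled.
3. Leave the care-cost row as a two-part model: probability from the yes/no item, mean cost among payers.
4. Where the meaning of a 0 cannot be settled from the raw answer, report a sensitivity analysis under the rule as printed.
5. Multiply the travel-time loss by observed clinic visits, as the fare rule does. In the telerehab arm add set-up time × video sessions attended × hourly income.

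The cost is revised wording in the cleaning table and Table 2 and a few lines of code. The survey answers, attendance, travel time and set-up time are already collected. The one limit is that some raw zeros may stay ambiguous, which item 4 covers.

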Annex 1: Program schedule

Visit no.	Standard program		Telerehabilitation program	
	Test/Intervention	Time (min)	Test/Intervention	Time (min)
ASSESSMENT PHASE				
Visit 0	First Paediatrician visit Screening for ASD (DSM-5) Initiate informed consent taking for study (refer to consent form) – can be done at Visit 0 or 1			30
Visit 1	Second Paediatrician visit Initiate informed consent taking for study (refer to consent form) – can be done at Visit 0 or 1 Refer for ADOS and MSEL if consent is given Otherwise continue with standard care			30
Visit 2-3	Nurse Assessment MSEL + PSI			120
	Psychologist Assessment ADOS + VABS			120
Visit 4	Third Paediatrician visit Paediatrician visit to share Mullen's & ADOS-2 report and confirm enrolment into the study and to inform arm of study. If patient does not meet the inclusion criteria. They will be referred to standard care outside the trial.			30

Visit 5	Therapist Assessment (clinic based)			90
	
 • Foundational Skills Curriculum (FSC) assessment • Parent interview on routines • Joint engagement rating inventory (JERI) • Family Early Intervention Quality of life survey (FEIQoL) • Demographic survey • Cost Survey 			
			Preparation for video conferencing Video conferencing observation (FSC, NDBI-Fi)	30
Visit 6	Parent Education Workshop (Can be conducted either in person or through electronic training slides)			90
For eligible and chosen participants, pre-interview will be conducted between visit 5 and before the Intervention Phase.				45
INTERVENTION PHASE				
1 st block of intervention	Clinic-based intervention (CBI) x 6 (Commencement of Individualised intervention plan (IIP))	60 x 6	Clinic-based intervention (CBI) x 2 (Commencement of Individualised intervention plan (IIP))	60 x 2
			Video conference-based intervention (VCBI) x 4	45 x 4
Parent-delivered therapy home-based)				
2 nd block of intervention	Clinic-based intervention (CBI) x 4	60 x 4	Video conference-based intervention (VCBI) x 4	45 x 4

Visit 7-8	Fourth Paediatrician visit Midpoint Review by paediatrician (clinic based or teleconsultation)			30
	
 • Child's profile, progress • Child and Family's needs • Appropriate recommendations and referrals (if needed) 			
	Midterm Progress Review with Therapist (clinic based)			60
	
 • Foundational skills curriculum – Child's development profile • Joint Engagement Rating Inventory (JERI) • Cost Survey 			
Parent-delivered therapy (home-based)				
Visit 9	Midpoint IIP Review with Therapist (clinic based)	60	Midpoint IIP Review with Therapist (clinic based)	60
3 rd block of intervention	Clinic-based intervention x 6	60 x 6	Video conference-based intervention (VCBI) x 2	45 x 2
	Parent-delivered therapy (home-based)			
Visit 10-11	Fifth Paediatrician visit Midpoint Review by paediatrician (clinic based or teleconsultation)			30
	
 • Child's profile, progress • Child and Family's needs • Appropriate recommendations and referrals (if needed) 			
	Review with Therapist (clinic based)			60
	
 • Foundational skills curriculum – Child's development profile • Joint Engagement Rating Inventory (JERI) • Cost Survey 			

4 th intervention block	Parent-delivered therapy (home-based)	Video conference-based intervention (VCBI) x 6	45 x 6
		Parent-delivered therapy (home-based)	
Visit 12-14	Final Review with Therapist (clinic based)		90
	
 • Foundational skills curriculum (FSC) assessment • Joint engagement rating inventory (JERI) • Family Early Intervention Quality of life survey (FEIQoL) • Cost Survey 		
	Additional Indicators to baseline:		
	
 • Parent Satisfaction Survey 		
	Final Nurse Assessment (clinic based)		120
	
 • MSEL & PSI 		
	Final Psychologist Assessment (teleconsultation)		60
	
 • VABS-III 		
		Video conferencing observation (FSC, NDBI-Fi)	30
Visit 15	Sixth Paediatrician visit (final visit)		30
	Paediatrician to share reports and discuss progress and further needs of child and family		
Post-interview will be conducted for eligible and chosen participants after intervention is completed, or after participant has transitioned to EIPIC.			45
End of study			

